6.4 Overall Survival (OS)

Due to limited overall survival follow-up, only the number and percentage of all deaths will be presented.

6.5 Clinical Benefit Rate by Gene Mutations

The concordance between gene mutations detected by local and central labs will be summarized on protocol pre-defined mutations. A frequency summary will be provided for summarizing clinical benefit rate per gene mutation using mutation data provided by the central lab (on protocol pre-defined mutations only) as well as by the local lab. The data will also be presented in a listing. This analysis will be performed for the FAS.

7 Safety evaluation

7.1 Adverse events

Adverse events data will be collected at each visit. They will be assessed according to the most current version of the Common Toxicity Criteria for Adverse Events (CTCAE). If CTCAE grading does not exist for an adverse event, the severity of mild, moderate, severe,

and life-threatening, or grades 1-4 were used. CTCAE grade 5 (death) was not used in this study; rather, this information was collected in the End of Treatment/Study or Survival Information CRF page.

All AEs will be coded by Preferred Term (PT) and associated primary System Organ Class (SOC) using MedDRA (Medical Dictionary for Regulatory Activities, version 19.0 or above). The CRF collects the verbatim term for MedDRA coding.

Summaries of AE will be based on treatment emergent adverse events (TEAEs), which is defined as all new or worsening events collected from first study treatment date to last treatment date + 30. Novartis standard partial date imputation methods will be used for imputation of partial AE onset/resolution dates.

Analysis of Adverse Events

In general, the subject incidence of TEAEs will be summarized for all tables, unless otherwise noted, by SOC and PT. TEAEs will be shown in alphabetical order for SOCs and in decreasing frequencies for PTs within each SOC. Subject frequencies and percentages will be presented.

All summaries will be based on subject counts (i.e., the number and percentage of subjects who satisfy the criteria), and will depict all AEs and all grade 3/4 AEs at minimum. Each subject will be counted at most once per category. For subjects with multiple grades for the same event, only the worst grade will be counted.

The following summary tables will be provided for the SS:

- Summary of TEAEs by SOC, PT, and maximum severity
- Summary of serious TEAEs by SOC and PT
- Summary of the most common TEAEs (10% or more of subjects) by PT and decreasing frequency
- Summary of suspected TEAEs by SOC and PT
- Summary of TEAEs associated with permanent discontinuation of study drug
- Summary of TEAEs associated with dosage adjusted/temporarily interrupted of study drug
- Summary of adverse events of special interest (see details below in Section 7.1.1)

Individual records of AEs will also be listed alphabetically by the SOC/PT and then in chronological order (i.e., by start date of the event as recorded in the CRF). The listing will include subject identifier, age, race, gender, and all related event status information (e.g., grade, relationship to study medication, etc.). For the overall AE listing, AEs that are non-treatment emergent will be included. Separate AE listings that include only TEAEs (e.g., suspected AEs, serious TEAEs) will also be presented.

7.1.1 Specific safety event categories

Specific Safety Event Categories (SEC) consists of adverse events for which there is a specific clinical interest in connection with ceritinib treatment (i.e. where ceritinib may

influence a common mechanism of action responsible for triggering them) or adverse events which are similar in nature (although not identical).

Each of these SECs uses MedDRA categories (Standard MedDRA Query [SMQ], Novartis MedDRA Query [NMQ], High Level Group Term [HLGT], etc.) to group preferred terms for which there is a specific clinical interest. One SEC can be defined by one or several MedDRA categories. These SECs are defined in the current version of the ceritinib Safety profiling plan/ceritinib Case Retrieval Strategy (CRS) document.

Standard data of analysis for all SECs will be conducted as follows:

- The number and percentage of subjects will be reported by SEC, by MedDRA category and by preferred term.
- All AEs of subjects having at least one AE in that SEC will be listed.

7.2 Deaths

A subject listing of deaths with recorded principal cause of death (if available) will be provided.

7.3 Vital signs

Actual raw values and changes from baseline for vital sign results (sitting systolic and diastolic blood pressure, sitting pulse, body temperature, respiratory rate, and weight) obtained for each scheduled visit will be summarized using descriptive statistics (number of subjects, mean, standard deviation, median, 25th percentile, 75th percentile, minimum, and maximum). Baseline is defined as the last non-missing measurement prior to the first ceritinib dose. Vital signs will also be presented in a listing. These analyses will be performed using the SS.

7.4 Laboratory evaluations

Laboratory assessment will be collected at screening and post baseline (at scheduled visits outlined in the protocol or as clinically indicated). The collected laboratory values will be converted into standard units and the severity grade will be calculated using CTCAE v4.03. A severity grade of 0 will be assigned when the value is within normal limits. For laboratory parameters where severity grades are determined both through normal limits and absolute cut-offs, in the unlikely case that a local laboratory normal range overlaps into the higher (i.e., non-zero) CTCAE grade, the laboratory value will still be taken as within normal limits and assigned a CTCAE grade of zero. Baseline is defined as the last non-missing measurement on or prior to the first ceritinib treatment. On-treatment laboratory evaluations are defined as laboratory values collected post baseline and no later than 30 days after the last study treatment.

Abnormal on-treatment laboratory values will be summarized using shift tables (from baseline to any abnormal laboratory value post baseline) by each laboratory parameter at its worst severity grade. The number and percentage of subjects with abnormal laboratory values will be presented by CTCAE grade for each laboratory parameter that is CTCAE gradable. For laboratory parameters where CTCAE grades are not defined, shift tables using the

low/normal/high/(low and high) classification to compare baseline to the worst on-treatment value will be provided. Listings of all laboratory values (Blood chemistry, Hematology/Coagulation parameters separately) in chronologic order will be provided for each laboratory parameter. Laboratory values collected more than 30 days after study treatment discontinuation will be flagged in the listing. A separate listing will also be provided for notable laboratory abnormalities (i.e., grade 3 or 4 laboratory toxicities post start of study treatment). In addition, other labs such as urinalysis and pregnancy tests will be listed separately. These presentations will be performed for the SS.

7.5 Other safety evaluations

ECOG performance status will be summarized by visit for SS. The number and percentage of subjects in each score (0-5) will be displayed. In addition, the shift table of ECOG value from baseline to the worst score post baseline will be presented.

ECG values will be summarized descriptively by visit for the SS. Change from baseline for each collected parameter will also be summarized. The ECG parameters to be summarized include: QTcF, HR, PR, QT, and QRS.

Cardiac imaging evaluations will only be listed.

Baseline for the safety evaluation is defined as the last non-missing measurement on or prior to the first ceritinib dose.

8 Interim analyses

Scheduled interim analysis is planned for the primary endpoint of clinical benefit rate only as required by the Bayesian Hierarchical design. The first interim analysis performs after the first 30 patients have been dosed for at least 16 weeks or discontinued then every 13 weeks thereafter until study enrollment closure. After that, one CBR analysis will be done after database lock. Interim analyses may be performed more frequently dependent on enrollment rate to avoid over-enrollment in any of the disease groups. At each interim analysis, the groups will be evaluated for early futility and early success by comparing posterior quantities for the response rate to pre-specified early stopping criteria.

There is no plan for a formal interim analysis of safety or other secondary endpoints for this study. However, for publication or other purposes, interim data review of clean data will be performed as necessary. At these interim reviews, patient demographics/baseline characteristics, the primary and secondary endpoints as applicable, and all important safety endpoints will be summarized. No formal report will be issued for these interim data reviews.

9 Determination of sample size

The sample size was chosen by the usual criteria of obtaining adequate power for the alternative hypothesis of interest as shown in the protocol Tables 4.2 of Appendix Q (same as Table 2 as shown below in Section 10.4.2). This hypothesis corresponds to a generally effective treatment across groups and incorporates variation in treatment effects to reflect the realistic expectation that treatment effects may differ by group. In this setting, analytical power calculations are not possible, but the design was simulated to obtain the power of the

study as shown in Section 10 below. The sample size shown (minimum of 10 for futility stopping, minimum of 15 for early success and maximum of 30 as group cap) achieve adequate power for the alternative hypothesis. The simulations included the expected variable accrual by simulating a Poisson process with expected accrual also shown in the protocol Appendix Q (same as Section 10 below).

Given the exploratory nature of the study design, there is no power consideration for secondary objectives.

10 Bayesian Adaptive Design

10.1 Introduction

This document outlines the adaptive design for Novartis's P2P trial of LDK378.

This trial will enroll patients from at least 6 histologic groups:

- Breast
- Colorectal
- B-Cell Lymphoma
- Melanoma
- ALCL
- Ovarian

In addition, another group currently simply referred to as "Other" may be identified and enrolled throughout the study (e.g. "Other" will be a focused histologic group, but may not be explicitly identified until the trial is ongoing due to recruitment issues). We discuss the logistics in more detail below, but a decision will only be made for a group other than the 6 listed if 1) more than 3 patients are enrolled in the group, and 2) a reasonable estimate of the clinical benefit rate is available.

The primary endpoint is clinical benefit rate (CBR) in each group, with clinical benefit being assessed at 16 weeks. All patients will be assigned LDK378.

10.1.1 Primary Analysis

We let Y_i be the response indicator for the i^{th} subject, and let R_g be the assumed probability of response within a control population and $\pi_g = \Pr(Y_i = 1 | g_i = g)$ be the underlying probability of response for group g within the treatment group. We transform to the logit scale for modeling purposes. Let θ_g be the mean log odds treatment effect, i.e.:

$$\theta_g = \log\left(\frac{\pi_g}{1 - \pi_g}\right) - \log\left(\frac{R_g}{1 - R_g}\right).$$

Thus, θ_g is the group specific logistic regression coefficient for the treatment within group g . The primary analysis is a set of group specific tests that $\theta_g > 0$, meaning that the treatment is better than the assumed control rate within that group. Thus, we wish to test the set of hypotheses

$$H0g : \theta_g \leq 0$$

$$H1g : \theta_g > 0$$

We proceed in a Bayesian fashion, assigning a prior distribution (discussed below) and computing the posterior probability of H_{1g} within each group g . If, at the final analysis,

$$\Pr(\theta_g > 0 | \text{data}) > 0.90$$

Then group g will be declared a success (thus, the final analysis produces a separate decision for each group). The trial also allows for early stopping of groups, described below.

10.1.2 Trial Logistics

The trial will enroll all available subjects in all groups for 2 years unless a group cap is reached or a group is stopped early. The trial will enroll no more than 30 evaluable subjects in each group. Interim monitoring will be conducted starting after the first 30 patients enrolled overall (across all groups) have been dosed for at least 16 weeks or discontinued, then continuing each 13 weeks thereafter. At each interim analysis, response information for the various groups will be evaluated to determine the current $\Pr(\theta_g > 0 | \text{data})$ within each group, with sufficiently high/low values used to stop the group for success/futility. A minimum of 10 patients will be required in a group before it may discontinue enrollment for futility, and a minimum of 15 patients are required before discontinuing a group for efficacy. If a group stops enrolling early, the remaining groups will continue until the end of 2 years or until the other groups reach their own early stopping criteria. The final analysis will occur after 2 years of trial duration, with all subjects enrolled at 2 years followed up to their endpoint.

The trial will enroll subjects in all listed groups. In addition, should other groups be identified throughout the trial, the following mechanism will be used. If another group is identified, it will not be placed into the statistical analysis unless 3 subjects enroll within the group (thus, the trial may enroll multiple possible groups within the “other” category, but a group will only be added to the list if at least 3 patients enroll from that group. Thus, it is possible (but not viewed as likely) that multiple “other” groups may be added to the trial if the trial has sufficient enrollment in multiple “other” groups. In addition to sufficient enrollment, the sponsor must have a reasonable estimate of the control clinical benefit rate.

Subjects within the “other” category which do not reach the minimum 3 subject enrollment will be excluded from the interim and final analyses. Thus, in the statistical analysis below, the number of groups may be 4 (if no other groups meet the requirements for inclusion in the study) or more if other groups are identified throughout the course of the study. As the study continues, early interim analyses may be based on fewer groups than later interim analyses, as the interim analyses will include whatever groups have satisfied the criteria at the time of the analysis.

10.2 Statistical Modeling

We let Y_i be the response indicator for the i^{th} subject, and let R_g be the probability of response within a control population and $\pi_g = \Pr(Y_i = 1 | g_i = g)$ be the underlying probability of response for group g within the trial. We transform to the logit scale for modeling purposes. Let θ_g be the mean log odds treatment effect, i.e.:

$$\theta_g = \log\left(\frac{\pi_g}{1 - \pi_g}\right) - \log\left(\frac{R_g}{1 - R_g}\right).$$

The statistical design borrows information across groups with a hierarchical model. The hierarchical model allows dynamic borrowing of information between groups such that more borrowing occurs when the groups are consistent and less borrowing occurs when the groups differ. In this way, the model is a compromise between the two alternate extremes of either a completely pooled analysis or a separate analysis in each group. We additionally incorporate a clustering mechanism that allows borrowing within clusters but treats clusters separately. This minimizes borrowing across groups that are quite different in terms of CBR.

The purpose of such an analysis is to produce higher power or lower type I error in situations where we see some commonality (identical effects are not required) among the groups. The model will borrow more in situations where the groups appear similar than situations where the groups appear different.

10.2.1 Hierarchical Model with Clustering

Our hierarchical approach involves two stages. The goal of both stages is to allow the data to drive the amount of borrowing across groups. If the data indicate a large amount of borrowing is appropriate (due to similar results), the model will borrow more and thus increase the overall power of the trial within each group. In contrast, if the data indicate a small amount of borrowing is appropriate (due to dissimilar results) the model will adjust and each group will stand more on its own. This “dynamic” borrowing property is distinct from other approaches which use a fixed informative prior or *apriori* assume an amount of borrowing across groups. Here the approach includes two stages to identify the appropriate amount of borrowing based on the data.

The first stage of model places the groups into distinct clusters. The purpose of this stage is to minimize borrowing of information across groups that appear to be quite different. Thus, for example, should 2 of the groups appear similar while the others differ significantly, the model may place a large probability on two clusters, one containing the two similar groups with the other containing the remaining groups. The model incorporates the uncertainty of the data in this determination, producing a probability distribution over the possible clusterings. Thus, in our example, the model may consider it highly likely that the 2 similar groups are in one cluster with the remaining groups in another, but it would also retain lower probabilities on the possibility all groups are in one cluster (e.g. we are simply seeing differences in the two groups by chance) as well as other possibilities. The complete analysis averages over this uncertainty. This clustering approach is implemented through a Dirichlet Process Mixture (DPM) model, described in the appendix.

At the second stage, we place hierarchical models over the groups within each cluster (thus, conditional on the clustering, there is no borrowing of information across clusters, only within clusters). The hierarchical model assumes that the θ_g have an across groups distribution

$$\theta_g \sim N(\mu, \tau^2)$$

The across group mean μ and variance τ^2 are unknown, and hence have a prior distribution which is combined with the data to produce estimates of μ and τ^2 .

The variance component τ controls the degree of borrowing among groups. Small values of τ result in a greater degree of borrowing while large values of τ correspond to less borrowing.

The parameter τ is estimated using the data, so the observed between group variation is a key component of the model behavior.

Combined, the two stages allow groups with similar results to borrow information between them (they will have a high probability of being in the same cluster) while groups with different results will borrow far less information between them (they will have a low probability of being in the same cluster).

Details of the two stages may be found in the appendix.

10.3 Evaluation of Trial Success and Futility

Interim monitoring will occur after the first 30 patients, then every 13 weeks thereafter. At each interim analysis, the groups will be evaluated for early futility and early success by comparing posterior quantities for the response rate to pre-specified early stopping criteria.

10.3.1 Early Futility

If there is less than 10% probability that the response rate in a group exceeds the historical rate R_g , then the group will stop enrollment early for futility. Formally, enrollment will stop early for futility if:

$$\Pr(\pi_g > R_g) < 0.10.$$

A group is only eligible for early stopping once a minimum of 10 patients has been evaluated for response in that group.

10.3.2 Early Success

If there is at least 95% probability that the response rate in a group exceeds the historical rate, then the group will stop enrollment early for success. Formally, enrollment will stop early for success if:

$$\Pr(\pi_g > R_g) > 0.95.$$

A minimum of 15 subjects will need to be evaluated prior to declaring a group to be efficacious.

10.3.3 Final Analysis

In addition, recall the final analysis will occur when both accrual and follow-up are complete in all groups. If, at the completion of the trial, there is at least 90% probability that the response rate in a group exceeds the historical rate, then the group will be considered a success. Formally:

$$\Pr(\pi_g > R_g) > 0.90.$$

10.4 Simulation

We evaluated type I error and power for each of the 7 possible groups (including one “other” category) under a variety of possible “truths” indicating various possible true underlying probabilities within each group. Note as described above the 7th “other” group is only included in the analysis if it enrolls at least 3 subjects.

10.4.1 Assumptions

Accrual - Table 1 shows the assumed two year expected accrual number as well as the assumed control rates for the 7 histologic groups (including “other”). Note these are averages, the actual number of available patients is simulated as a Poisson distribution with the specified mean. Also note that the group cap of 30 applies, and thus if the number of available patients in a group exceeds 30, only the first 30 available patients in that group will be enrolled in the study. Note given the low assumed enrollment rate for “other” (2), there is a high likelihood these subjects will not enroll sufficiently to enter the main analysis.

Dropouts – We assume no dropouts for the purpose of this simulation.

Control Rates – Table 1 also shows the assumed control rates.

Histology	Assumed 2 year accrual	Assumed Control Rate (R_g)
Breast	20	0.69
Colorectal	15	0.26
B-cell Lymphoma	6	0.60
Melanoma	8	0.30
ALCL	6	0.90
Ovarian	15	0.65
Other (where applicable)	2	0.50

Table 1 – Assumed 2 year accrual rates (accrual is simulated as a Poisson process with these means) and assumed control CBR values used in the simulations.

We consider four possible scenarios, or possible “truths” in the simulation. These consisted of a null scenario (where the treatment has no effect for any group), an alternative scenario (where the treatment is effective in all groups), a scenario where the treatment was effective in two of the groups, and a scenario where the treatment was effective in half of the groups.

Treatment Rates - The treatment rates for each scenario are shown in the table below. Values identical to the control are shown in bold, while values greater than the assumed control rate are shown in italics.

	Null	Alternative	Two	Half
Breast	0.69	0.88	0.88	0.69
Colorectal	0.26	0.50	0.26	0.50
B-cell Lymphoma	0.60	0.82	0.60	0.60
Melanoma	0.30	0.55	0.55	0.55
ALCL	0.90	0.97	0.90	0.90
Ovarian	0.65	0.85	0.65	0.85
Other (where applicable)	0.50	0.75	0.50	0.75

Simulation Details – For each scenario we simulated 1000 trials. For each interim within each trial, we ran 50,000 MCMC iterations after a 1,000 MCMC iteration burnin.

10.4.2 Results

Table 2 below provides the probability of group success for each of the groups

Group (Exp N)	Null	Alternative	Two	Half
Breast (20)	0.126	0.924	0.815	0.246
Colorectal (15)	0.059	0.813	0.116	0.743
B-cell Lymphoma (6)	0.063	0.692	0.125	0.180
Melanoma (8)	0.052	0.698	0.517	0.627
ALCL (6)	0.003	0.611	0.045	0.148
Ovarian (15)	0.082	0.839	0.151	0.771
Other (where applicable) (2)	0.011	0.509	0.069	0.294

Entries in bold represent groups where the treatment effect is 0 (e.g. the treatment is ineffective). Thus, entries in bold are type I errors. Entries in italics appear where the treatment is effective, and thus indicate the power of the design.

Generally, type I error is controlled at 0.10 under the null scenario (the borrowing compensates for the multiple interim analyses) and power is an increasing function of the expected sample size (power for Breast, Colorectal, and Ovarian are generally high, particularly in the alternative case). In the alternative scenario there remains decently high probability of success even in the lower enrolling groups. When fewer groups are effective in truth, the scenarios “half” and “two” are harder to discern, however the model still retains around 75-80% power to isolate the highest enrolling groups. In these scenarios identifying the lower enrolling groups becomes more problematic, with power between 50-65%.

Power is reduced and type I error is inflated when the truth is a mixture of effective and ineffective treatment effects across the groups. Generally power again is a function of the sample size.

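### SAP Table 2 prints 0.509 power for the 'Other' group, which cannot be a proportion of all simulated trials under the SAP's own three-subject entry rule, and the text's 50-65% range leaves out that group's 0.294

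*SAP*

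**What the plan says.** SAP Section 10.4.1 (Table 1) gives the 'Other' group an assumed two-year accrual of 2 and a control rate of 0.50. It states that "the actual number of available patients is simulated as a Poisson distribution with the specified mean". The group's true rate is 0.75 in the Alternative and Half scenarios and 0.50 in Null and Two.

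SAP Section 10.4 says the seventh "group is only included in the analysis if it enrolls at least 3 subjects". SAP Section 10.1.2 says that subjects in this category "which do not reach the minimum 3 subject enrollment will be excluded from the interim and final analyses". SAP Section 10.1 is stricter: a decision is made for an added group only if "more than 3 patients are enrolled in the group". SAP Section 10.4.1 also warns that "there is a high likelihood these subjects will not enroll sufficiently to enter the main analysis".

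Table 2 in SAP Section 10.4.2 reports the probability of group success from 1000 simulated trials per scenario. The row "Other (where applicable) (2" reads 0.011 (Null), 0.509 (Alternative), 0.069 (Two) and 0.294 (Half). The text below the table says that in the Two and Half scenarios the lower-enrolling groups are harder to identify, "with power between 50-65" per cent. SAP Section 9 relies on this table for its statement that the sample sizes give adequate power under the alternative hypothesis.

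**The concern.** A group that is left out of the analysis cannot be declared a success. Its unconditional success probability is therefore capped by its probability of entering, and 0.509 looks too high for a group with mean accrual 2 and a minimum of 3. It also sits badly with the SAP's own remark that the group will probably not enter.

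The 'Other' row is the only evidence in SAP Section 10 on how the design performs for a tumour type added during the trial. Taken at face value, it offers about an even chance of detecting an effective added group. The sentence after the table also describes the low-enrolling groups more favourably than the table does.

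**Working it through.** **Chance of entry.** With N ~ Poisson(2):

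- At least 3: P(N ≥ 3) = 1 − e⁻²(1 + 2 + 2) = 1 − 5e⁻² = 0.323.
- More than 3: P(N ≥ 4) = 1 − e⁻²(1 + 2 + 2 + 4/3) = 0.143.

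The unconditional success probability cannot exceed these values, even if every entering group succeeds.

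**Could 0.509 be simulation noise?** At 1000 trials, the standard error at the ceiling is √(0.323 × 0.677 / 1000) = 0.0148. Then (0.509 − 0.323) / 0.0148 ≈ 12.6 standard errors. It could not.

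**What the printed row may represent.** The design was rebuilt twice with separate code: Poisson accrual; Dirichlet process clustering with α = 2; τ² ~ IG(3, 0.5); and the final rule in SAP Section 10.3.3 that "there is at least 90% probability that the response rate in a group exceeds the historical rate". The SAP does not say whether 1.82 in the prior for μ is a variance or a standard deviation, so both were tried. One rebuild used 3000 trials per scenario and the other 800 to 1500. The ranges below span both rebuilds and both readings of the prior.

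| 'Other' | Null | Alternative | Two | Half |
|---|---|---|---|---|
| Printed in Table 2 | 0.011 | 0.509 | 0.069 | 0.294 |
| Entry rule (≥ 3) applied, all trials | 0.01-0.03 | 0.18-0.21 | 0.03-0.04 | 0.14-0.16 |
| Conditional on N ≥ 3 | 0.04-0.07 | 0.54-0.62 | 0.10-0.12 | 0.43-0.46 |
| Three-subject rule not applied | 0.01-0.03 | 0.43-0.50 | 0.05-0.07 | 0.23-0.29 |

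The last line is closest to the printed row. The conditional line is nearest in Alternative but misses in Half (0.43-0.46 against 0.294). Without the rule, groups with fewer than 3 patients still succeed in about 38-44% of trials in Alternative in the second rebuild, through borrowing from the other groups.

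The rebuild is not an exact reproduction. With 1.82 as a standard deviation, most named groups in Alternative fall within about 0.02 of Table 2: Colorectal 0.83 against 0.813, Ovarian 0.86 against 0.839, Breast 0.90-0.91 against 0.924. ALCL is lower, at 0.57-0.59 against 0.611. Some Half entries differ by 0.05-0.07.

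**Unconditional power on each reading, entry at 3 or more.**

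- Printed values conditional on entry: 0.509 × 0.323 ≈ 0.165 (Alternative) and 0.294 × 0.323 = 0.095 (Half).
- Rule omitted and now applied: about 0.18-0.21 and 0.14-0.16.

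If entry needs more than 3, neither can exceed 0.143.

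**The 50-65% sentence.** By the treatment-rate table in SAP Section 10.4.1, the effective groups in Two are Breast (expected N 20) and Melanoma (8). In Half they are Colorectal (15), Melanoma (8), Ovarian (15) and 'Other' (2). The effective lower-enrolling entries are therefore Melanoma, 0.517 and 0.627, and 'Other', 0.294. The printed range is about 29-63%. The stated range describes Melanoma alone.

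**Named groups.** In the second rebuild, switching the entry rule on or off changes the six named groups by at most 0.013.

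**The case against.** The strongest reply is that Table 2 gives no denominator and that the row label can be read as conditional on entry. On that reading 0.509 breaks no ceiling. This stands as far as it goes: a reader might infer that 0.509 is impossible outright, and the documents do not establish that. They show only that it is not a proportion of all trials if the entry rule was applied. The conditional reading is still weak. The row carries the unconditional expected N of 2, Table 1 uses the same label for the unconditional accrual, and nothing marks this row as different from the others. The mismatch in Half is the best evidence against it, but that evidence comes from a rebuild.

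A reader might also infer that the simulation left out the entry rule, or that the true power is 0.19. Neither is supported as fact. The code is not in the documents and the rebuild fits only approximately; one of its two versions approximated 'no rule' with a minimum of one patient. A single value near 0.19 also presumes entry at three. Under the more-than-three wording it would exceed the 0.143 ceiling.

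On importance, the reply is largely right. The SAP warns that this group will probably not be analysed, the named groups barely move, no decision threshold depends on the row, and SAP Section 2 records that the study was terminated early. The current protocol Appendix Q also simulates eight other cohorts with no mean-2 'Other' group, a wider mismatch that correcting this row would not cure.

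The 50-65% sentence can be called loose prose with the 0.294 in plain view above it. It is nevertheless contradicted by the printed table, whatever the denominator.

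**Conclusion.** The point holds in limited form. Given Poisson accrual of mean 2 and entry at three or more, 0.509 exceeds the 0.323 chance of entering and cannot be an unconditional success probability. On either reading consistent with that rule, unconditional power in Alternative is far below 0.51: about 0.17 if the printed figure is conditional, or about 0.18-0.21 by re-simulation with the rule applied. It would be lower still if entry needs more than three. The ceiling rests only on the SAP's stated inputs. The 0.18-0.21 rests on a rebuild that matches Table 2 approximately, and the 0.17 on taking the printed value as conditional.

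The 50-65% range is wrong against the table as printed, which supports about 29-63%. The effect is confined to the optional 'Other' row and the sentence describing it. It does not undermine the power shown for the six named groups.

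**What to change.** 1. Reconcile the entry rule first: SAP Section 10.1 requires more than 3 subjects, Sections 10.1.2 and 10.4 at least 3. Protocol Appendix Q has the same split (4 or more in Section 14.17.1, 3 in Section 14.17.1.2).
2. Re-run Table 2 with the reconciled rule applied, or state that the 'Other' row is conditional on entry. Give the denominator either way.
3. For 'Other', report the probability of entering, the probability of success given entry, and their product.
4. Replace 50-65% with the range the table supports: about 29-63% on the present figures, to be updated after any re-run.
5. State whether 1.82 in the prior for μ is a variance or a standard deviation, so that the table can be reproduced.

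The cost is one simulation re-run and a few sentences in SAP Section 10. One stated power becomes less favourable, and no analysis or decision threshold changes unless reconciling the entry minimum changes which added groups are analysed.
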